### Diabetes history

Time since diagnosis of diabetes 1 (based on date of informed consent and start date of diabetes 1) (years) will be tabulated with descriptive statistics by treatment group. If the day is not available, the calculation of duration will be based on month and year only, setting the start day to 1. In case only the year is available, the start day will be 1 and the start month will be January.

### Body measurements

Separate descriptive statistics will be presented for body measurements (height, weight, BMI) by treatment group.

### Medical history

The verbatim term of the medical history condition/event will be coded using Medical Dictionary for Regulatory Activities (MedDRA), version 22.0.

A summary will be prepared by treatment group. The summary will show the system organ class and preferred terms ordered by descending order of incidence of system organ class and preferred term within each system organ class.

Demographic and baseline characteristics will be summarized for the safety analysis set and FAS. If the safety analysis set and FAS are identical, then it will be sufficient to state this in the table output section.

### Other information documented at screening

Analyses of other screening or baseline variables as listed below, which are documented at screening/baseline and/or have further evaluations after the screening/baseline visit will be described in subsequent sections.

- Physical examination
- Vital signs
- 12-lead electrocardiogram (12-lead ECG)
- Central safety laboratory (hematology, biochemistry, coagulation, urinalysis)
- Antibody serum sample for immunogenicity measurements

## 9.5 Concomitant Medications and Current Diabetes Treatment

Concomitant medication and current diabetes treatment verbatim terms in the eCRFs will be mapped to Anatomical/Therapeutic/Chemical (ATC) class and preferred names using the WHODrug Global (version March 2018).

All concomitant medications and current diabetes treatment will be listed as documented in the eCRF. In this listing the WHODrug coding including the drug name as documented in the eCRF, the drug name used for the coding, the preferred term, the ATC code and the ATC term will be included as well.

Coding will be done using ATC level 4, which will be presented in the listings.

Concomitant medications and current diabetes treatment will be summarized for each treatment by WHO ATC class (level 2) and preferred name. These summaries will present the number and percentage of patients using each medication. Patients may have more than 1 medication per ATC class and preferred name. At each level of patient summarization, a patient is counted once if he/she reported 1 or more medications at that level. Each summary will be ordered by descending order of incidence of ATC class and preferred name within each ATC class.

In case the centers also captured true prior medications, this will only be listed and a flag will be included in the raw data listing denoting whether the medication is prior or concomitant.

The distinction between previous and concomitant medication will be done as follows:

- Prior medication is all medication which stopped before the first investigational medicinal product (IMP) administration within the trial context, independent from start date.
- Concomitant medication is all medication that started prior to the first IMP administration and is still ongoing or stopped at date of first study drug intake - or medication that started at/after the date of the first drug intake.
- If the start or stop date is incomplete and the allocation to previous or concomitant is not clear, the medication will be considered to be concomitant.

## 10. EFFICACY ANALYSES

The primary efficacy analysis will be based on the FAS. Analogous supportive sensitivity analyses will be conducted in the PPS, but without inference intent.

## 10.1 Efficacy Variables

The **primary** efficacy variable is:

- Time to plasma glucose recovery. Plasma glucose recovery is defined as first increase in plasma glucose of  $\geq 20$  mg/dL (1.1 mmol/L) from baseline during the hypoglycemic clamp procedure without administration of rescue intravenous (IV) glucose. Time to recovery is considered only within the first 45 minutes from baseline. In this trial, plasma glucose for pharmacodynamics is reported with the unit 'mmol/l'. For consistency, these results are converted into the unit 'mg/dl' by using the conversion factor 0.0555 (i.e. Glucose [mg/dl]=Glucose [mmol/l] /0.0555).

**Secondary** efficacy variables include the following:

- Plasma glucose recovery within 30 minutes, within 20 minutes, within 15 minutes, and within 10 minutes after study drug injection without administration of rescue IV glucose.
- Plasma glucose changes from baseline at 30 minutes, at 20 minutes, at 15 minutes, and at 10 minutes after study drug injection or at the time of rescue IV glucose.

## 10.2 Baseline Values

Unless otherwise noted, baseline is defined as the last non-missing value recorded prior to the first dose of study drug. Unscheduled visits will be used in the determination of baseline values, when applicable.

## 10.3 Adjustments for Covariates

The model for the primary efficacy will include adjustments for the following covariates:

- Age group: 6-11 years, 12-17 years
- Injection site: abdomen/thigh

## 10.4 Handling of Dropouts or Missing Data

Only non-missing cases will be analyzed, ie, no imputation technique like last observation carried forward will be applied. Summaries will be based on observed data only.

## 10.5 Interim Analysis and Data Monitoring

There are no planned interim analyses for this study.

---

 For simplification the addition 'during the hypoglycemic clamp procedure' will be omitted further on.

## 10.6 Examination of Subgroups

No subgroup analysis is planned.

## 10.7 Multiple Comparison/Multiplicity

For the confirmatory analyses of the primary and secondary endpoints, patients treated with either dasiglucagon 0.6 mg and or placebo will be compared. A hierarchical procedure will be applied for the control of multiplicity. The primary and secondary endpoints will be evaluated on the FAS.

For the confirmatory analyses, the following a priori-defined hierarchical inferential test order will be applied for the control of the type 1 error rate across the planned multiple comparisons. The primary endpoint and secondary endpoints will be inferentially evaluated within the FAS in the following order, where inference will proceed at the 2-sided 0.05 criterion significance level until the first failure to reject the null hypothesis for a dasiglucagon versus placebo comparison:

- Primary: Time to plasma glucose recovery
- Secondary 1-4: Plasma glucose recovery within 30 minutes, within 20 minutes, within 15 minutes, and within 10 minutes after study drug injection without administration of rescue IV glucose.
- Secondary 5-8: Plasma glucose changes from baseline at 30 minutes, at 20 minutes, at 15 minutes, and at 10 minutes after study drug injection or at the time of rescue.

The GlucaGen® versus placebo comparisons will not be included in the inferential testing hierarchy, since the efficacy of GlucaGen® is previously established, and these comparisons are intended to support the validity of the study for the dasiglucagon versus placebo comparisons. Moreover, the comparison of dasiglucagon versus GlucaGen® is not part of this hierarchical testing procedure.

## 10.8 Multicenter Studies

This is a multicenter study, having approximately 5 centers participating in the study. The factor center will not be accounted for in the primary statistical analysis model.

## 11. METHODS OF EFFICACY ANALYSIS

### 11.1 Primary Efficacy Analyses

The primary endpoint, time to plasma glucose recovery, will be summarized using Kaplan-Meier estimates per treatment group.

The actual time points at 0, 4, 6, 8, 10, 12, 15, 17, 20, 30, 45 and 60 minutes will be used in the analyses.

Kaplan-Meier plots will be created showing the the estimated survival function for each treatment in one plot.

In the primary analysis, recovery cannot be achieved in those subjects where rescue IV glucose treatment is administered. Those subjects who receive rescue IV glucose will be censored (and set to 'not recovered') at 45 minutes after dosing.

For patients who did not recover within 45 minutes after dosing, time to recovery is censored at 45 minutes.

The stratified log-rank test will be applied to compare the dasiglucagon 0.6 mg treatment group to the placebo group. The same method will be applied to compare dasiglucagon 0.6 mg with GlucaGen®, but not considered for the confirmatory hierarchical testing procedure.

In order to facilitate this, SAS procedure proc lifetest is used. The following code will be used, but minor variations can be applied during programming:

```
proc lifetest data=xx plots=survival(atrisk=0 10 15 20 30 45);  
  time aval * Status(0);  
  strata age site/ group= treat test=logrank diff=all;  
run;
```

where "aval" is the time to plasma recovery, and "status" is a censor variable for patients who receive IV glucose. Age group and injection site are the stratification variables and "treat" the planned treatment assignment.

The unstratified result of the log-rank test can be obtained from the following code:

```
proc lifetest data=xx plots=survival(atrisk=0 10 15 20 30 45);  
  time aval * Status(0);  
  strata treat / test=logrank diff=all;  
run;
```

In sensitivity analyses, the time to plasma glucose recovery will be analyzed

- 1) without censoring for those subjects who require rescue IV glucose before 45 minutes and
- 2) with censoring at the time of administration of rescue IV glucose before 45 minutes.

As a supportive analysis to the stratified log-rank test for the time to plasma glucose recovery, dasiglucagon will be compared to placebo using a Wilcoxon test stratified by age group and injection site.

To graphically describe recovery in time, a histogram showing the proportion of patients that recovered at each time interval will be created, one for each treatment group.

The primary endpoint will additionally be analyzed using a discrete-time Cox proportional hazards (CPH) time to event statistical model, if the hazards by treatment group can be assumed

proportional using a graphical comparison of log-minus-log survival curves and no more than two-thirds of the recovery times are censored in each treatment group. The CPH model will be used for descriptive purposes, with treatment group, age group and injection site modeled as categorical effects, and baseline plasma glucose modelled as a continuous covariate. The treatment group hazard ratios of active versus placebo, will be estimated together with the 95% confidence intervals, and pairwise treatment group inferences (dasiglucagon vs placebo, GlucaGen vs placebo, dasiglucagon vs GlucaGen) will be evaluated using least-square mean and standard deviation estimates.

Due to the discrete nature of blood sampling in time, and the fact that there must be a true, but unmeasured, ordering of the recovery times, the method using the “exact discrete” partial likelihood for tied failure times will be applied. In SAS, this is implemented in the `phreg` procedure with the option `ties=discrete`. The influence of age and injection site on time to recovery will also be evaluated in the proportional hazards model by a ‘type 3’ test in the `phreg` procedure.

In addition, separate CPH models will be calculated to evaluate homogeneity for the following factors:

Sex, BMI class, ethnicity, race, US/non-US.

These additional homogeneity models are only presented for the primary efficacy analysis, but not for subsequent variants of that analysis.

To obtain an estimate of these true, but unassessed, patient recovery times, a linear interpolation (between the two time points before and after recovery is observed) will be carried out to estimate the patients’ actual time of recovery. These derived recovery times will be described and analysed in the same manner as for the discrete times above.

Let  $t_1$  and  $t_2$  be the 2 time points before and after recovery is observed and  $y_1$  and  $y_2$  be the corresponding changes from baseline in glucose concentrations, where  $y_1$  is below 20 mg/dL and  $y_2$  is greater than 20 mg/dL.

The interpolated time point  $t_{ext}$  is calculated then as:

$$t_{ext} = t_1 + \frac{(20 - y_1) * (t_2 - t_1)}{(y_2 - y_1)}$$

This linear interpolation is only used as a supportive analysis to the primary analysis model using `proc lifetest`.

In this statistical model, `ties=exact` will be used.

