## 11.2 Secondary Efficacy Analyses

The secondary efficacy endpoints are plasma glucose recovery within 10, 15, 20 and 30 minutes after trial product injection, ie, achieving a  $\geq 20$  mg/dL increase in plasma glucose from baseline at 0 to 10, 15, 20, and 30 minutes.

Actual timepoints of sampling will be used for this calculation.

If a patient has received an IV glucose treatment before recovery, the patient is set to “not recovered” in the analysis of the 4 endpoints, corresponding to censoring in the time-to-recovery analysis for the primary endpoint. The 10-, 15-, 20-, and 30-minute recovery rates of dasiglucagon and Placebo will be compared by a Cochran-Mantel-Haenszel test stratified by age group and injection site. The treatment responder rates with the 95% confidence intervals will be presented for the 10-, 15-, 20-, and 30-minute endpoints.

If due to small or zero cell counts the Cochran-Mantel-Haenszel test fails, non-stratified Fisher exact tests will be applied instead.

Plasma glucose changes from baseline at 10, 15, 20, and 30 minutes after trial product injection will be analyzed in an analysis of variance with factors treatment (3 levels), age group (2 levels), and injection site (2 levels) for each endpoint. If the rescue IV glucose was administered before 10, 15, 20, or 30 minutes, respectively, the patient’s plasma glucose changes from baseline will be determined from the value at the time of rescue IV glucose administration.

The change from baseline is calculated using the nominal sampling time.

Least-square mean adjusted treatment means will be presented with their 95% confidence intervals including the 95% confidence intervals for the treatment difference. The analysis of variance at each of the 4 time points will also be used to test the difference of dasiglucagon and Placebo adjusted for age group and injection site.

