PT Term 1	xx ( xx.x) xx	xx ( xx.x) xx	xx ( xx.x) xx	xx ( xx.x) xx
PT Name 2	xx ( xx.x) xx	xx ( xx.x) xx	xx ( xx.x) xx	xx ( xx.x) xx
PT Name 3	xx ( xx.x) xx	xx ( xx.x) xx	xx ( xx.x) xx	xx ( xx.x) xx
PT Name xx	xx ( xx.x) xx	xx ( xx.x) xx	xx ( xx.x) xx	xx ( xx.x) xx
ATC class xx				
PT Name 1	xx ( xx.x) xx	xx ( xx.x) xx	xx ( xx.x) xx	xx ( xx.x) xx
PT Name 2	xx ( xx.x) xx	xx ( xx.x) xx	xx ( xx.x) xx	xx ( xx.x) xx
PT Name 3	xx ( xx.x) xx	xx ( xx.x) xx	xx ( xx.x) xx	xx ( xx.x) xx
PT Name xx	xx ( xx.x) xx	xx ( xx.x) xx	xx ( xx.x) xx	xx ( xx.x) xx
...				

Note: At each level of summation (overall, ATC class, preferred name) patients reporting more than 1 medication/ treatment are counted only once.  
Table is sorted by descending total patient count  
Percentages are based on total no. of subjects in each treatment group

PROGRAM SOURCE:###, DATA CUT OFF DATE: ddmmyyyy

RUN DATE: ddmmyyy hh:mm CET

14.2.1.1: Time to plasma glucose recovery - summary table, FAS

Primary model

	Treatment			p-values
	dasiglucagon (N=xxx)	GlucaGen (N=xx)	placebo (N=xx)	
Status (N)	Xx	xx	xx	
Recovered 	xx (xx.xx)	xx (xx.xx)	xx (xx.xx)	
Censored 	xx (xx.xx)	xx (xx.xx)	xx (xx.xx)	
Time to recovery (minutes)				
25th percentile	xx.x	xx.x	xx.x	
Median (95% CI)	xx.x (xx.x ; xx.x)	xx.x (xx.x ; xx.x)	xx.x (xx.x ; xx.x)	
75th percentile	xx.x	xx.x	xx.x	
Dasiglucagon versus Placebo P-value (log-rank test - stratified)				x.xxxx
P-value (log-rank test - non-stratified)				x.xxxx
P-value (Wilcoxon test) - stratified				x.xxxx
Dasiglucagon versus GlucaGen				
P-value (log-rank test - stratified)				x.xxxx
P-value (log-rank test - non-stratified)				x.xxxx
Cox proportional hazards 				
Hazard ratio	xx.xx	xx.xx	1	
95% profile CL	(xx.xxx ; xx.xxx)	(xx.xxx ; xx.xxx)		
P-values				
Dasiglucagon versus Placebo				x.xxxx
Dasiglucagon versus Glucagen				x.xxxx
Glucagen versus Placebo				x.xxxx
Type 3 test for Age				x.xxxx
Type 3 test for injection site				x.xxxx

1: Increase of plasma glucose of 20 mg/dL within 45 min without iv glucose

2: Did not recover within 45 min or received iv glucose before 45 min

3: Cox proportional hazard model with treatment, age and injection site as fixed effects and baseline plasma glucose as covariate

[figure not shown]
Homogeneity models

	Treatment		
	dasiglucagon (N=xxx)	GlucaGen (N=xx)	placebo (N=xx)
Cox proportional hazards 			
			
Hazard ratio	xx.xx	xx.xx	1

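### Read literally, the primary rescue rule cancels a recovery that came before rescue IV glucose, which SAP 11.2 does not do (minor)

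*SAP*

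**What the plan says.** **Primary endpoint.** SAP 11.1 states that "recovery cannot be achieved in those subjects where rescue IV glucose treatment is administered" and censors these patients at 45 minutes as not recovered. It describes the status variable as one that "is a censor variable for patients who receive IV glucose". Protocol 10.1.3.2 and the Appendix C comment to Table 14.2.1.1 also depend only on receipt of IV glucose. In the Table 14.2.1.1 layout (SAP Appendix D), footnote 1 defines recovered as "Increase of plasma glucose of 20 mg/dL within 45 min without iv glucose" and footnote 2 defines censored as "Did not recover within 45 min or received iv glucose before 45 min". Footnote 2 limits rescue by clock time but not by its order relative to recovery.

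**Secondary endpoints 1-4.** SAP 11.2 says: "If a patient has received an IV glucose treatment before recovery, the patient is set to" not recovered. It adds that this is "corresponding to censoring in the time-to-recovery analysis for the primary endpoint". Protocol 10.1.3.3 has the same condition and the same cross-reference.

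**Sensitivity analyses.** SAP 11.1 repeats the primary analysis "without censoring for those subjects who require rescue IV glucose before 45 minutes" and then "with censoring at the time of administration of rescue IV glucose before 45 minutes".

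**Related text.** SAP 10.1 considers time to recovery only within the first 45 minutes. Protocol 10.1.3 has a further sentence that places the censoring of rescued patients at the time of glucose recovery. SAP 15 reports that the primary analysis was reworded, but does not mention the order of rescue and recovery or that sentence.

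**The concern.** SAP 11.2 says its rule corresponds to the primary censoring, but the primary rule as written is different. The secondary rule asks whether rescue came before recovery. The primary rule asks only whether rescue was given. An observed primary event can therefore be overwritten by something that happens after it.

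The same status variable feeds the counts, quartiles and tests in Table 14.2.1.1. The stratified log-rank test comes first in the hierarchy of SAP 10.7, ahead of all eight secondary tests. If the question came up after unblinding, someone who knew the allocation would be deciding who counts as recovered.

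**Working it through.** **1. The plan's own figure.** Inputs (SAP 5, protocol 10.2): exponential times, medians 10 and 50 minutes, 20 versus 10 patients, 45 minutes of follow-up, two-sided 5%.

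- Hazards: ln2/10 = 0.0693 and ln2/50 = 0.0139; difference 0.0555.
- Recovered by 45 minutes: 1 − 2^(−4.5) = 0.956 and 1 − 2^(−0.9) = 0.464.
- Variance of the difference: 0.0693²/(0.956 × 20) + 0.0139²/(0.464 × 10) ≈ 0.000293; standard error 0.0171.
- Power: Φ(0.0555/0.0171 − 1.96) = Φ(1.28) = 0.90.

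The stated 90% is reproduced. The calculation contains no rescue rule, so clarifying that rule does not change it.

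**2. The two rules applied to the same children** (times invented):

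| Child | Primary rule, literal | Secondary rule | Sensitivity 1 | Sensitivity 2 |
|---|---|---|---|---|
| Recovers at 10 min, never rescued | event at 10 | recovered | event at 10 | event at 10 |
| Rescued at 12, rises by 20 mg/dL at 20 | censored at 45 | not recovered | event at 20 | censored at 12 |
| Recovers at 10, rescued at 30 | censored at 45 | recovered within 10, 15, 20 and 30 | event at 10 | event at 10* |

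*By the usual convention that the earlier of event and censoring counts; the SAP does not say so.

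Only the third child is treated differently by the primary and secondary rules. The usual convention does not settle that child's primary status, because the primary censoring time is fixed at 45 minutes and not at rescue. Every rise within the window comes no later than 45 minutes, so the convention alone would also keep the second child's rise.

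**3. Can the third child occur?** Dosing requires glucose of at least 54 and below 80 mg/dL (protocol 7.4.5.2.2), so recovery means at least 54 + 20 = 74. Before 45 minutes, protocol 7.4.5.2.3 calls for rescue if glucose is below 54 between 8 and 44 minutes, or at any time for escalating symptoms. After recovery, the glucose route needs a fall of more than 74 − 54 = 20 mg/dL. The case is possible, and the documents give no frequency for it.

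**4. Illustration only.** 40,000 simulated trials per model used 20 versus 10 patients, the planned sampling times to 45 minutes and a log-rank test over four strata. Randomly chosen recovered patients were recoded as censored at 45 minutes. Placebo times are exponential with median 50 (mean 4.6 of 10 recover). Model A is the exponential planning model for dasiglucagon (mean 19.1 of 20 recover). It leaves 0.5^2.7 = 15% of times beyond 27 minutes, whereas the longest phase 2 times in protocol 5.1 were 15 to 27 minutes across doses. Model B is therefore lognormal with median 10 and an assumed 97.5% recovered by 27 minutes (mean 19.97 of 20).

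| Recoded (dasiglucagon, placebo) | Power, model A | Power, model B |
|---|---|---|
| 0, 0 | 0.890 | 0.965 |
| 1, 0 | 0.806 | 0.924 |
| 2, 0 | 0.688 | 0.845 |
| 0, 1 | 0.951 | 0.986 |
| 1, 1 | 0.906 | 0.967 |

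One recoded dasiglucagon recovery costs about 4 to 8 points, one recoded placebo recovery adds about 2 to 6, and one in each arm costs nothing.

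**The case against.** The best defence is that the plan already contains the order rule. SAP 11.2 states it and says that the primary censoring works the same way. The endpoint definition, a first increase without rescue, is most naturally a rise achieved unaided. The sentence in SAP 11.1 can be read as looking forward: a child who recovered at 10 minutes has already achieved recovery, and only a later rise is ruled out. The status description is plainly shorthand, since it also omits unrescued children who never recover. Any discrepancy would show up in the sensitivity analyses and in secondary endpoints 1-4.

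Much of this stands. The intent is reasonably clear, and the status description and footnote 1 are weak evidence for a literal rule. It does not dispose of footnote 2, which makes IV glucose before 45 minutes sufficient for censoring and would be programmed that way. The endpoint definition can be read either way on rescue after recovery. The sensitivity analyses could reveal an effect, but neither supplies the confirmatory p-value.

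A reader might also infer that rescue at or after 45 minutes, where glucose below 70 mg/dL is enough, could erase many recoveries, because SAP 11.1 sets no time limit on rescue. The documents do not support that. SAP 10.1 confines the endpoint to 45 minutes, and footnote 2 and both sensitivity analyses concern rescue before 45 minutes. That limit only needs repeating in SAP 11.1.

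**Conclusion.** Minor, but wrong as written. The literal primary rule and the secondary rule disagree for any patient who recovers and is then rescued before 45 minutes, although the plan says they correspond. The conclusion rests on the text alone.

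Its practical size is unknown and may be nil. If no child is rescued after recovery, the two rules give identical results. A reader might take the simulation as a forecast loss of 4 to 8 points of power, or as a bias against dasiglucagon. Neither follows: the recoded patients were inserted by assumption, and the effect reverses or cancels depending on the arm.

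**What to change.** Before unblinding, state the following in SAP 11.1 (text and status description), the Appendix C comment and the Table 14.2.1.1 footnotes:

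- Event: the first rise of at least 20 mg/dL from baseline within 45 minutes of dosing and before any post-dose rescue IV glucose.
- Patients rescued before such a rise, or with no such rise by 45 minutes, are not recovered and are censored at 45 minutes.
- Rescue IV glucose after recovery does not change the event.

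Use these footnotes only for tables that apply the primary rule. The layouts of Tables 14.2.1.5 and 14.2.1.7 are specified as repeats of Table 14.2.1.1, so the new footnotes would carry over and contradict sensitivity analysis 1. Give those two tables their own footnotes, matching sensitivity analyses 1 and 2. Record the change in SAP 15, and note there that it supersedes the protocol 10.1.3 sentence placing censoring at the time of glucose recovery.

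The cost is text edits only, with no new data. Protocol 10.1 lets the SAP adapt the analysis before unblinding, so the protocol text need not be edited. No change to the clinical rescue criteria is proposed.

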At all dose levels in the phase 2 trial, all patients achieved a plasma glucose level of at least 70 mg/dL as well as an increase in plasma glucose by at least 20 mg/dL within 30 minutes post-dose. The maximal observed time to reach the 20 mg/dL plasma glucose increase ranged from 15 to 27 minutes across doses and decreased as the dose increased. The PD responses of 0.6 mg of dasiglucagon and 1.0 mg of GlucaGen® were comparable.²

Safety of dasiglucagon

The safety data for dasiglucagon did not give rise to any relevant safety concerns for dasiglucagon beyond those expected, related to the pharmacological effect of glucagon receptor agonism. All adverse events (AEs) recorded in the trials were of mild or moderate severity. The most frequently reported systemic AE was nausea, which is a known side effect following administration of glucagon. Headache was the next most frequently reported event, occurring in all dose groups in the phase 2 trial. Injection site reactions were observed only sporadically after administration with either dasiglucagon or GlucaGen® and all were mild and transient. The most frequent injection site reaction was erythema, occurring in all treatment groups, including the placebo group, irrespective of dose. Therefore, the phase 1 and 2 results and the safety profile described to date do not give rise to specific safety concerns. For further information, please refer to the Investigator Brochure.²

Immunogenicity of dasiglucagon

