## 5. DETERMINATION OF SAMPLE SIZE

The primary comparison is between the dasiglucagon and placebo treatment arms. From phase 2 results, the median time to an increase of 20 mg/dL of the 0.6 mg dose was approximately 10 minutes. For placebo-treated patients, the median time to recovery is assumed to be more than 50 minutes. Assuming an exponential time-to-recovery distribution with median times of 10 and 50 minutes, a 2-sided log-rank test will be able to detect a difference between dasiglucagon 0.6 mg

and placebo with 90% power with a follow-up time of 45 minutes at a 5% significance level with 20 patients randomized to the dasiglucagon arm and 10 patients to placebo.

GlucaGen® is included as a reference to compare the responses and AE profile to dasiglucagon with those to a marketed product. It is expected that 10 patients in the GlucaGen® group will suffice for the comparison.

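### The log-rank code in SAP 11.1 is not restricted to the two arms being compared; if run as written it would tilt dasiglucagon v GlucaGen towards dasiglucagon and cost the primary test about 3 points of power

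*SAP*

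**What the plan says.** SAP 11.1 states the confirmatory test in words: "The stratified log-rank test will be applied to compare the dasiglucagon 0.6 mg treatment group to the placebo group". The same method is to be used for dasiglucagon v GlucaGen, outside the testing hierarchy. SAP 10.7 likewise describes the confirmatory comparison as one of dasiglucagon and placebo patients. SAP 5 rests its power on a two-arm test: "Assuming an exponential time-to-recovery distribution with median times of 10 and 50 minutes, a 2-sided log-rank test", with "90% power with a follow-up time of 45 minutes at a 5% significance level" and "20 patients randomized to the dasiglucagon arm and 10 patients to placebo".

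The code that SAP 11.1 says will be used, subject to small changes in programming, has the line "strata age site/ group= treat test=logrank diff=all" on a placeholder data set. The unstratified call also carries `diff=all`. Neither has a `WHERE` clause, and no sentence says that the data set holds only two arms. The same section wants every treatment in one Kaplan-Meier plot, and the shell of Table 14.2.1.1 has three treatment columns with both log-rank contrasts beneath them. SAP 15 declares no three-arm contrast.

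**The concern.** The option `diff=all` is needed only when there are more than two groups, so the natural reading of the code and the table shell together is one three-arm run from which both contrasts are taken. In a joint log-rank test the expected counts come from the pooled risk set of all arms. A contrast between two arms then depends on the third arm, and it differs from the two-arm test that the text names and SAP 5 powers.

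Two things are at stake. The confirmatory p-value would depend on GlucaGen children, who are not part of its hypothesis. The log-rank comparison with GlucaGen, planned in support of the secondary objective that the two products are comparable, would lean towards dasiglucagon because dasiglucagon has twice as many patients.

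**Working it through.** **Inputs.** From SAP 5: exponential recovery times, medians 10 and 50 min, 45 min follow-up, two-sided 5%, 20 dasiglucagon, 10 placebo, 10 GlucaGen. From SAP 11.1: four strata (two age groups by two injection sites), the plasma glucose sampling times, censoring at 45 min. Assumed, because the documents do not give it: a GlucaGen median of 10 min, varied from 5 to 15 min. The reason for the central value is Protocol 5.1: "The PD responses of 0.6 mg of dasiglucagon and 1.0 mg of GlucaGen® were comparable". Also assumed is the form of the `diff=all` statistic in step 2.

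**1. The plan's own figure.** Expected recoveries by 45 min are 20 × (1 − 2^(−45/10)) = 19.1 and 10 × (1 − 2^(−45/50)) = 4.6. A two-arm log-rank calculation with expected risk sets (Lakatos method) gives a drift of 3.244, so power = Φ(3.244 − 1.960) = 90.0%. The stated 90% is reproduced.

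**2. Why the three-arm contrast is off centre.** For arm k, U_k = Σ(d_k − d·n_k/n), with covariance matrix V. The pairwise statistic is z = (U_a − U_b)/√(V_aa + V_bb − 2V_ab). If arms a and b share hazard h, the mean of U_a − U_b accumulates as (n_a − n_b)(h − h̄), where h̄ is the pooled hazard of all three arms. This is zero only if the two arms are the same size or the third arm has the same hazard.

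Take dasiglucagon and GlucaGen both at median 10 min. At time zero h = ln2/10 = 0.0693 and h̄ = (30 × 0.0693 + 10 × 0.0139)/40 = 0.0555. The contrast gains (20 − 10) × 0.0139 = 0.139 per minute in dasiglucagon's favour. Over 45 min the expected observed-minus-expected counts are +6.15 (dasiglucagon), +3.07 (GlucaGen) and −9.22 (placebo), and the drift between two identical arms is 0.72 standard errors.

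For dasiglucagon v placebo the same method gives a drift of 3.082, so power = Φ(3.082 − 1.960) = 86.9%.

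**3. Primary power, like for like** (GlucaGen median 10 min; 10,000 to 14,000 simulated trials per simulated row):

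| Calculation | Two-arm | Three-arm contrast |
|---|---|---|
| Expected risk sets, unstratified | 90.0% | 86.9% |
| Simulated, sampling grid, unstratified | 92.7% | 89.6% |
| Simulated, sampling grid, stratified | 88.9% | 86.1% |
| Simulated, continuous time, stratified | 87.8% | 84.8% |

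The loss is about 3 points in every row.

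Dependence on the GlucaGen arm (stratified, grid, placebo median 50 min; 6,000 trials each, 14,000 at 10 min):

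| GlucaGen median | Two-arm | Three-arm contrast |
|---|---|---|
| 5 min | 88.8% | 78.1% |
| 7 min | 88.6% | 82.0% |
| 10 min | 88.9% | 86.1% |
| 15 min | 89.3% | 90.0% |

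Repeat runs put the three-arm figure at about 77-78% for 5 min and 88-90% for 15 min.

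Dependence on placebo (GlucaGen median 10 min; 3,000 trials each), three-arm v two-arm: 94.9% v 96.7% at a placebo median of 75 min, 98.3% v 98.8% at 100 min, 99.7% v 99.9% at 200 min.

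**4. Dasiglucagon v GlucaGen** (stratified, grid, dasiglucagon median 10 min, placebo median 50 min):

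| GlucaGen median | Rejects in favour of | Two-arm | Three-arm contrast |
|---|---|---|---|
| 10 min (equal) | dasiglucagon | 2.2% | 4.1% |
| 10 min (equal) | GlucaGen | 3.4% | 0.08% |
| 5 min | GlucaGen | 35.7% | 1.4% |
| 15 min | dasiglucagon | 14.0% | 22.8% |

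Under equality about 98% of the three-arm rejections, 4.13/(4.13 + 0.08), favour dasiglucagon. Total error is 4.2%. A normal calculation from the 0.72 drift alone would suggest Φ(0.722 − 1.960) = 10.8% in that direction. The simulated rate is lower because the joint variance treats all three arms as having one hazard and so overstates the spread of this contrast. Separate simulations gave 4.5% v 0.15% under equality, and detection of the twice-as-fast GlucaGen arm in 1.6% v 34.1% and 1.8% v 36.5% of trials.

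**5. False efficacy in the primary test.** With dasiglucagon equal to placebo and GlucaGen active, rejections favouring dasiglucagon were 0.17% and 0.3% in two simulations; those against it were 5.2% and 6.2%. With all three arms equal, both methods reject in about 5.5% of trials with no material tilt.

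**The case against.** The strongest reply is that the text governs and is right. The code is a template on a placeholder data set, small changes are allowed, and a programmer could add the restriction. Nor do the documents say how `diff=all` forms its statistic. Both points stand as limits: a reader might infer that the trial will certainly be analysed by a three-arm contrast, and the documents do not establish that. They also state no restriction, and the option and the table shell point the other way. A choice that alters the confirmatory p-value should be fixed before unblinding.

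A reader might also infer that primary power drops from the planned 90% to 86%. Like for like the loss is about 3 points. The step from 90.0% to 88.9% is present in the stratified two-arm test too, and the fix does not recover it. SAP 5 assumes a placebo median of more than 50 min, so 50 is the boundary case, and rescued children count as not recovered, which pushes placebo further that way. Protocol 5.1 reports that all phase 2 patients had the 20 mg/dL rise within 30 min, whereas an exponential with median 10 min leaves 2^(−3) = 12.5% unrecovered by then. The base case is probably pessimistic.

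Finally, dasiglucagon v GlucaGen is outside the hierarchy, and other evidence does not use this contrast: Kaplan-Meier medians with confidence intervals, responder rates by arm, and the Cox model. That is fair, as is the point that a non-significant log-rank test with 10 GlucaGen patients cannot show comparability in either version. But the Cox model is planned only if no arm has more than two-thirds of times censored. At a placebo median of 100 min the expected censored share is 2^(−45/100) = 73%, so it may be absent exactly when placebo recovers slowly.

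**Conclusion.** Wrong as written, and worth correcting. Provided `diff=all` works from the joint three-arm statistic, the code does not deliver the tests that SAP 11.1 names.

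The main harm is to dasiglucagon v GlucaGen. Under equality nearly all false rejections favour dasiglucagon (about 4-5% v 0.1%), and a GlucaGen arm twice as fast would be seen in about 2% of trials instead of about 36%. It would be too strong to say that all errors favour dasiglucagon or that total error is inflated: in the base case it stays at about 4-5%. The defect is in direction and sensitivity.

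For the primary test the cost is about 3 points of power at an assumed GlucaGen median of 10 min, more if GlucaGen is faster, none at about 15 min, and negligible if the placebo median is well above 50 min. A reader might infer a risk of a false efficacy claim. The calculations do not support that: when dasiglucagon equals placebo and GlucaGen works, the contrast leans against dasiglucagon.

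**What to change.** In SAP 11.1, run each log-rank test in its own call, with a `WHERE` restriction to dasiglucagon and placebo for the primary test and to dasiglucagon and GlucaGen for the second. Do this for the stratified and the unstratified versions, and drop `diff=all` from all four calls. Carry the same restriction into the sensitivity and per-protocol tables that repeat Table 14.2.1.1. Keep one three-arm call solely for the Kaplan-Meier plot and estimates. Before the blind is broken, run both forms on a test data set to confirm how `diff=all` behaves.

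If the three-arm contrast is in fact intended, say so in SAP 11.1 and SAP 15 and recompute the power with a stated GlucaGen median. The preferred change costs a few lines of code and needs no new data, patients or change in design.
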